#### 1. INTRODUCTION

#### 1.1. BACKGROUND

#### Children and Young People's Mental Health

Children and young people (CYP) are highly susceptible to mental disorders due to developmental changes in emotion, behaviour and cognition, with over 75% of mental disorders emerging before age 25 (Kessler et al., 2005). The worldwide prevalence of mental disorders in CYP is estimated to be 13.4%, and anxiety, depression, and eating and sleep disorders are prevalent issues among CYP globally (Polanczyk et al., 2015; GBD 2019, 2022). In the United Kingdom (UK), one in four CYPs is estimated to have a probable mental disorder (NHS Digital, 2023). However, more than 70% of CYPs with mental health problems do not receive treatment (Henderson et al., 2013). The increased burden on the NHS and the commitments made in the NHS Long Term Plan (NHS, 2019) demand access to cost-effective and evidence-based methods to provide mental health support to CYP at scale.

#### Mobile Mental Health Apps and Artificial Intelligence

With the widespread use of smartphones among CYP (Ofcom, 2022), digital health interventions are an attractive, cost-effective, and scalable solution for mental health prevention and early intervention in CYPs. In the last ten years, there has been a surge in the usage of mental health apps (Larsen et al., 2019). There are now over 20,000 mental health apps available on the App Store/Android equivalent. Systematic reviews and meta-analyses provide evidence of the positive impact of mental health apps on mental health outcomes (Dubaud et al., 2018; Lecomte et al., 2020; Linardon et al., 2024), and qualitative studies show that CYP think mental health apps are acceptable (Dewa et al., 2019). However, most mental health apps are not empirically validated, lack long-term engagement and do not involve CYP in their development, remaining insufficiently tailored to their needs.

There is a significant relationship between lifestyle factors such as exercise, diet and sleep and mental disorders (Firth et al., 2020). Active and passive sensing have become common in digital monitoring technologies for mental health. Active sensors can collect subjective data through repeated self-reports of emotions and behaviours (active data), while passive sensors collect objective data by detecting changes in the physical environment without user participation (passive data), including GPS, accelerometer, microphone and battery usage. Active and passive data represent digital behavioural markers as they can be used to model individuals' mental health states in their contextual and temporal dimensions (Oudin et al., 2023). Based on this data, Ecological Momentary Interventions (EMI) can deliver personalised behaviour change support in real-time and in natural settings (Balaskas et al., 2021). A subset of EMIs, just-in-time adaptive interventions (JITAD), can be delivered in the moment and tailored in terms of time of delivery.

Artificial Intelligence (AI) and Machine Learning (ML) present new opportunities for real-time interventions. A systematic review of 17 studies examined the feasibility of using AI-enabled mobile solutions using active and passive data to support mental health (Milne-Ives et al., 2022). Across the 17 studies, the most common use of AI was to predict mental health outcomes, provide natural language support, and develop risk profiles. Only 2 studies used AI/ML to deploy context-sensitive notifications (Morrison et al., 2017) and CBT-based JITADs (Wahle et al., 2016). All studies were conducted in adults, with small sample sizes and short intervention durations. None of these studies was carried out in the UK. Only 3 studies were RCTs, and they had small sample sizes. Overall, AI/ML can be integrated into mental health apps, but the lack of evidence and weaknesses in study designs highlight the need for high-quality RCTs to demonstrate the effectiveness of AI-based apps in improving mental health.

#### MindCraft

MindCraft is an AI-based mental health app that combines active and passive tracking to monitor CYP's emotions and behaviour while encouraging user participation with a modern and appealing user interface (Kadirvelu et al., 2023). It is available for both IOS and Android. We conducted a pilot study of MindCraft that aimed to investigate the feasibility of using ML modelling to predict the risk of mental health problems in a non-clinical population of adolescent school children (PI: [name]; ICREC Reference number: 20IC6132) (Kadirvelu et al., 2025 JMIR preprint). These yet-unpublished findings support the use of ML to analyse combined datasets for early detection of mental health problems among CYP.

A new version of the MindCraft app has been developed in collaboration with CYP. This version features an AI-reinforced learning-based recommendation system designed to promote behavioural change and enhance CYP mental health. This system dynamically detects early signs of changes in mental health states from active and passive data collected through the app and responds by delivering personalised, instantaneous AI-informed recommendations ("nudges") (Figure 1). Intervention outcomes are measured in real-time and fed back to generate novel, individually tailored candidate nudges. This technology learns specific CYPs' emotional and behavioural profiles and contexts and recognises by "trial-and-error" successful from non-successful interventions.

[figure not shown]

Figure 1. Reinforcement learning-based recommendation system.

#### 1.2. RATIONALE FOR CURRENT STUDY

Internalising and externalising are two broad categories of behavioural problems, which in adolescence are associated with an increased likelihood of developing a psychiatric disorder later in adulthood (Copeland et al., 2009). While internalising problem behaviour is focused on the own self (e.g. withdrawal, anxiety, depression, emotional problems), externalising problem behaviour particularly occurs in interaction with the social environment (e.g. aggression, impulsivity, deviance, hyperactivity). School-based research suggests that the school environment plays a critical role in shaping students' behaviour and has a significant impact on CYP's health (Bonell et al., 2013). This makes schools well-placed to identify and address multiple determinants of mental health risk at the individual and community levels.

School-based interventions may be central to the early intervention and prevention of mental health problems in CYP. A recent meta-analysis showed a small positive effect of brief school-based interventions on mental health outcomes for up to one month, six months and one year (Cohen et al., 2025). In particular, digital mental health intervention programs offered in schools could present a readily accessible and flexible means for educating, empowering, and supporting adolescents in maintaining good mental health (Pandey et al., 2018). The integration of Al/ML offers the opportunity for individually tailored intervention. However, there is a lack of research on the efficacy of digital interventions, particularly those informed by Al/ML, on mental health outcomes in community CYP.

**Study Aim**: to examine the effectiveness of personalised AI-based recommendations ("nudges") on mental health outcomes in CYP within schools across the United Kingdom.

**Research Question**: Can Al nudges delivered through a mobile app improve CYP mental health in schools?

#### 2. STUDY OBJECTIVES

#### Primary objective:

 To examine the effectiveness of personalised AI nudges (experimental intervention) vs non-personalised digital self-help using generic CBT principles (active control) vs self-monitoring control on reducing CYP Strengths and Difficulty Questionnaire (SDQ) scores (primary outcome) at 1-month follow-up

#### Secondary objectives:

- To examine the effectiveness of personalised AI nudges vs non-personalised digital self-help using generic CBT principles vs self-monitoring control on secondary outcomes [Eating Disorder Diagnostic Scale (EDDS); Sleep Condition Indicator Questionnaire (SCI); Self-Injurious Thoughts and Behaviours Interview (SITBI); Self-Efficacy Questionnaire for Children (SEQ-C); World Health Organisation-Five Well-Being Index (WHO-5)] at 1-month follow-up
- To examine the efficacy of personalised AI nudges on improving mental health in CYP in a low-risk group (primary prevention) and reduce poor mental health in a high-risk group (secondary prevention) at 1-month follow-up
- To explore potential mediators and moderators of beneficial effects of Al nudges

**Hypothesis**: Al nudges will be more effective than non-personalised digital self-help using generic CBT principles (active control group) and self-monitoring control at reducing CYP SDQ scores at 1-month follow-up

#### 3. STUDY DESIGN

#### 3.1 Study Design and Timeline

The study will be conducted and reported according to Consolidated Standards of Reporting Trials (CONSORT) and CONSORT-EHEALTH for improving and standardising evaluation reports for mobile interventions (Eysenback, 2011). The trial will be registered on ClinicalTrials.gov (www.clinicaltrials.org).

The trial design is a 3-arm randomised controlled trial (RCT) conducted using a prospective cohort. Our study has been divided into an internal pilot phase and a main trial phase (Figure 2). We have conducted an internal pilot from October to May 2025 to test the quality of the trial design and the conduct of the study in relation to recruitment, adherence, outcome assessment, sample size and follow-up. Interim analyses were conducted to calculate the sample size needed for the main trial. We will also integrate any changes and release an improved version of the MindCraft app (e.g. correct bugs, upgrade systems and user interface). The duration of the main trial study will be roughly 8 months from recruitment to the end of data collection.

	2024			2025					2026						
	July -	Sept	Nov -	Jan -	March -	May -	July -	Sep	Nov	Jan -	March	May	July -	Sept	Nov
	Aug	Oct	Dec	Feb	April	June	Aug	Oct	Dec	Feb	April	June	Aug	Oct	Dec
Ethics application															
Ethics approval															
Internal Pilot															
Recruitment															
Data Collection															
Data Analysis															
Main Trial															
Recruitment															
Data Collection															
Data Analysis															

Figure 2. Gantt chart of the study.

In the main trial, all participants will join a prospective longitudinal cohort. Once trial eligibility has been determined and informed written consent to participate in the trial has been obtained, participants will be individually randomised (initially in a 1:1:1 ratio) into one of three arms:

- 1) Active experimental: Receipt of personalised Al-based recommendations within the MindCraft app in addition to self-monitoring
- 2) Active control: Generic psychoeducation recommendations using CBT principles within the app and self-monitoring through the app
- 3) Control: Access to self-monitoring through the app only

Given the rate of technological advancements of behavioural interventions, we will adopt the Trial of Intervention Principles methodology (Mohr et al., 2015), which focuses on the evaluation of intervention principles rather than a locked-down version of the intervention. This approach allows for ongoing quality improvement modifications to the behavioural intervention technology based on the underlying behavioural strategy while continuously improving the functionality of the technology without compromising trial integrity.

### 3.2 Randomisation, Intervention Delivery and Masking

Participants will be randomised (in a 1:1:1 ratio) to the three intervention arms and will be instructed to record data every day for four weeks. Stratification will be accounted for by considering SDQ scores to ensure balanced distribution of baseline characteristics.

Randomisation will be undertaken using a computer-based randomisation tool or software platform designed for clinical trials (such as https://www.sealedenvelope.com), ensuring unbiased allocation of participants across the three arms. Randomisation will be independent of the lead researcher.

Participants in the intervention and active control groups and the outcome assessor will be blind to intervention allocation.

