#### 3.4 Recruitment and Study Setting

We will recruit CYP in years 10 to 13 (age 14-19) attending schools in the United Kingdom. We aim to recruit around 5-10 schools, depending on how many students they accommodate. The research team will reach out to schools via email to the school principal/school staff and send information about the study. The research team will offer schools the option to learn more about the research and participate in educational activities related to mental health and digital interventions as part of the mandatory Social and Emotional Aspects of Learning (SEAL) framework.

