### 3.5 Screening and Consent Procedures

Potential participants will be informed about the study by their school. If data collection is carried out remotely, teachers will distribute information about the study via email to students and parents/guardians. Teachers will also send students a link to a Consent to Contact online form, where they will be asked to include their contact details and those of parents/guardians. On first contact with the students, the lead researcher ([name]) will email the full Participant Information Sheet and Consent/Assent Form to the students. Students over 16 will sign the Consent Form and email it back to the researcher. For any young person under 16, we will obtain informed parental consent by using opt-out consent (see Consent). The researcher

will send the Opt-out Consent Form to parents/guardians. Parents/guardians will sign and email back the Opt-out Consent Form to the researcher if they do not wish their child to participate. Parents will have at least two weeks to complete the opt-out form before any data is collected from children. Participants under 16 years old will also be required to provide written assent by signing the Assent Form and emailing it back to the researcher.

Alternatively, if the school prefers to carry out data collection in person on school premises, teachers will circulate the Participant Information Sheet to students and Parent/Guardian Information Sheet and Opt-out Consent Form for parents/guardians via email at least two weeks before the day of data collection. Students over 16 years old will provide informed consent electronically via Qualtrics on the day of data collection. They will also be asked to include their contact details and those of their parents/guardians. For participants under 16 years old, consent from a parent/guardian will be required for participation. Parents/guardians will sign and email back the Opt-out Consent Form to the researcher if they do not wish their child to participate. Parents will have at least two weeks to complete the opt-out form before any data is collected from children on school premises. Participants under 16 years old will provide written assent online via Qualtrics on the day of data collection.

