Participants will be followed up at 1 month. If data collection is carried out remotely, baseline and follow-up measures will be collected via an online Qualtrics questionnaire sent to the participant's email. If data collection is carried out in person, participants will complete the baseline (and follow-up) questionnaires through a Qualtrics link (separate from the Consent Form) on their mobile phones.

Completion of the baseline and outcome assessments should take a maximum of 30 minutes. No identifiable information will be collected. Participants will be assigned a unique participant ID, which they will use to complete the baseline and follow-up assessments and sign in to the study app (see Data Management section). Based on their ID, participants will be randomised to different versions of the MindCraft app (see Randomisation).

Reimbursement will be provided upon completion of the study, with the mode of reimbursement determined by each participating school. Schools may choose to distribute vouchers to students or receive the funds centrally to support researchand mental health—related activities, such as travel for workshops at Imperial.

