#### Primary analyses:

- Repeated measures analyses (using a mixed effects linear regression model with a random effect on participant) will be used to compare primary outcomes across follow-up points. Baseline SDQ scores will be included as covariates. The primary endpoint is the intervention difference at 1 month. As multiple analyses are performed to compare both the experimental interventions and the active control with the control, and to compare the experimental intervention with the active control, a multiplicity adjustment will be made with a Bonferroni correction. We will also carry out sub-analyses of primary outcomes based on participants' demographic characteristics/adding them as covariates in the MLM.

Secondary analyses:

- The same modelling approach as primary analyses will be used for secondary outcomes where possible.
- A Complier Average Causal Effect (CACE) analysis will be used to provide an estimate of intervention effect, accounting for pre-specified per-protocol adherence and compliance with the intervention while retaining the benefits of randomisation. Such models will be performed for the primary and secondary outcomes at 1-month follow-up using observed data only and will include the covariates adjusted for in the regression models.
- The pattern of missing outcomes will be examined, and multiple imputations will be used to impute primary and secondary continuous outcomes. Imputation models will be informed by treatment arm, baseline scores, other covariates to be included in the model, and other baseline characteristics found to predict outcome or propensity for missingness (logistic regression models will be used to investigate the associations between baseline characteristics and missingness). Results of imputed models will be compared to the primary analysis complete case ITT models. We will carry out sensitivity analyses to estimate the intervention effect, including all missing data.
- We will estimate the causal effect of the intervention using two-stage least squares (2SLS) regression to account for potential endogeneity in nudge exposure. Random assignment to treatment group (T1 or C2 vs. control) will be used as an instrument for actual exposure. The first stage will model nudge exposure as a function of assignment; the second stage will regress the outcome on predicted exposure. This approach will yield a local average treatment effect (LATE) among compliers. Robust standard errors will be used throughout.

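### School is recorded at baseline but is neither a stratification factor nor a term in the primary model: a modest, avoidable loss of precision and balance, not a source of bias

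*Protocol*

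**What the plan says.** Section 3.1 of the protocol makes the pupil the unit of allocation: "participants will be individually randomised (initially in a 1:1:1 ratio) into one of three arms". Section 3.2 names one stratifier: "Stratification will be accounted for by considering SDQ scores to ensure balanced distribution of baseline characteristics". Section 3.4 sets the number of sites: "We aim to recruit around 5-10 schools, depending on how many students they accommodate".

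Schools differ in how the trial is run. Section 3.5 provides for on-site assessment "if the school prefers to carry out data collection in person on school premises" and remote assessment otherwise. It also says reimbursement is given on completion, "with the mode of reimbursement determined by each participating school", either as vouchers to pupils or as funds held by the school.

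Section 3.6 lists school among the baseline demographics. Section 3.9 specifies the primary analysis "using a mixed effects linear regression model with a random effect on participant" and adds baseline SDQ as covariate. Demographic characteristics appear there only in connection with sub-analyses. For multiple imputation, the same section admits further baseline characteristics if they are found to predict outcome or missingness.

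On the order of events, section 3.5 says the participant ID is used to complete the baseline questionnaire, and then: "Based on their ID, participants will be randomised to different versions of the MindCraft app", with a pointer to the randomisation section.

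**The concern.** The protocol itself gives reasons to expect school to matter. Section 1.2 describes the school environment as important for pupils' behaviour and health. Section 3.3 allows usual practice to include support provided in school. Section 3.5 lets collection mode and reimbursement vary by school, and section 3.8 anticipates 40% attrition. School is therefore a plausible predictor of both the follow-up SDQ and whether it is completed.

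A predictor that is already collected and costs few degrees of freedom is normally used. Left out of the model, its variance goes into the residual and intervals are wider than they need be. Left out of the strata, the three arms can differ by chance within a school. The protocol states its stratifier and its primary model outright, so this is a choice it has made and not simply a detail left to a later plan.

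**Working it through.** **Inputs from the protocol.** Three arms, 1:1:1 (3.1); f = 0.139, alpha 0.05, power 80%, 505 participants before attrition, 40% attrition, 842 after (3.8); 5-10 schools (3.4). **Assumed:** a residual school ICC of 0.01-0.10, because the protocol gives none. Baseline SDQ is already in the model and should absorb some stable between-school difference, so the relevant value is the ICC after that adjustment.

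**Step 1: reproduce the stated size.** For a one-way three-group F test with noncentrality N × f², f = 0.139 gives N = 502 for 80% power, and power at 505 is 0.803. The stated 505 reproduces to within 1%. For attrition, 505 / (1 − 0.40) = 505 / 0.6 = 841.7, rounded up to 842, which matches.

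**Step 2: add school to the model.** If a share ICC of the outcome variance lies between schools, removing it gives f_adj = 0.139 / √(1 − ICC).

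| Assumed ICC | f_adj | N for 80% power | Saving against 502 | Power at 505 |
|---|---|---|---|---|
| 0 (school ignored) | 0.1390 | 502 | – | 0.803 |
| 0.01 | 0.1397 | 497 | 5 (1%) | 0.807 |
| 0.02 | 0.1404 | 492 | 10 (2%) | 0.811 |
| 0.05 | 0.1426 | 477 | 25 (5%) | 0.824 |
| 0.10 | 0.1465 | 452 | 50 (10%) | 0.845 |

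The 4-9 degrees of freedom for school are not deducted in this table. Against about 500 error degrees of freedom they hardly matter, and the simulation in step 3 does deduct them.

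**Step 3: is the test valid without school?** About 504 participants were simulated in 5 or 10 equal schools at ICC 0.02, 0.05 and 0.10, with 3,000 runs per cell for type I error. With allocation not stratified by school and school omitted from the model, type I error was 0.048-0.053, so the test keeps its level. In the 2,000-run power simulations at ICC 0.05, adding school moved power from 0.800 to 0.822 (5 schools) and from 0.798 to 0.820 (10 schools), in line with step 2.

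**Step 4: chance imbalance within a school.** With simple allocation, the average gap between the largest and smallest arm's share of a school is about 10 percentage points for 5 schools of 101 (95th percentile 19), and about 14 points for 10 schools of 50 (95th percentile 26). These sizes refer to the 505. Among the 842 randomised the gaps shrink by roughly √0.6 = 0.77, to about 8 and 11 points on average.

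**Step 5: stratify by school but leave it out of the model.** For a single two-sided contrast, the actual level is about 2 × [1 − Φ(1.96 / √(1 − ICC))]. This gives 0.049, 0.048, 0.044 and 0.039 at ICC 0.01, 0.02, 0.05 and 0.10. Simulated levels for the three-arm test at ICC 0.02-0.10 were 0.036-0.048. The test becomes conservative, so stratifying alone gives away part of the benefit.

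**The case against.** The strongest reply is that nothing here is invalid. Allocation is individual, so a school's collection mode and reimbursement apply to all three arms in that school and are not systematically related to arm. The gain depends on an ICC the protocol does not give, is small at plausible values, and is minor beside a 40% attrition allowance. A fuller covariate list could also appear in an analysis plan that is not shown. All of this stands as a limit on severity. It does not remove the point, because the stated strata and model leave out a collected variable that is cheap to use.

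Three stronger readings are tempting, and the protocol does not support them.

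- *Clustering in schools calls for a design effect.* That applies when schools are the unit of allocation. Here pupils are, and the simulated type I error confirms that no inflation arises.
- *School-related attrition goes unhandled.* Section 3.9 already brings into the imputation any baseline characteristic found to predict outcome or missingness, and school is one of those recorded. What remains is that the complete-case primary model omits school and that its place in the imputation is conditional.
- *The arm is fixed by the ID before the SDQ stratifier exists.* Section 3.5 ties app version to the ID but does not say the arm is set when the ID is issued. It refers back to the SDQ-stratified procedure, and section 3.3 describes the ID as the code needed to use the app. Section 3.1 randomises only after eligibility is determined, and the item for the sole exclusion criterion (4.3) is recorded in the baseline assessment (3.6) alongside the SDQ. That points to baseline first. The order is never stated, so one clarifying sentence is justified, but no failure of stratification is shown.

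**Conclusion.** The point holds as a matter of efficiency and balance. Leaving school out of the strata and the primary model causes neither systematic bias nor inflated type I error, and 505 and 842 stand. The cost is about 1-5% of the sample for an assumed residual ICC of 0.01-0.05 and about 10% at 0.10, together with avoidable chance imbalance of arms within schools. These figures rest on the assumed ICC, on schools of equal size, and on the three-group test that reproduces the protocol's sample size. The change is recommended but not essential. The order of ID, baseline SDQ and allocation is a minor matter of wording.

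**What to change.** - Add school as a fixed effect to the primary model in section 3.9. With 5-10 schools this uses 4-9 degrees of freedom.
- Name school as a variable that is always in the imputation model, so that its inclusion does not depend on a screening regression.
- If the allocation list is also stratified by school, together with SDQ, make that change and the model change at the same time (step 5). With two SDQ levels, an assumption, this gives 10-20 cells, or about 42 pupils per cell at 842 / 20. The model term is worth adding even if the list is left as it is.
- In sections 3.2 and 3.5, state that allocation is drawn after the baseline SDQ is submitted, and that the ID is only the login key to which the allocation is linked.

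The cost is one factor in the model, one setting in the randomisation tool if school strata are used, and a sentence of text. No new data are needed and the sample size does not change.
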